6.6 Recruitment and Consent

6.6.1. Sample Size

6.6.1.1 Service Users

The Esteem population includes ~250 service users, with ~150 new users per year. Around 80% would be expected to experience clinically significant sleep difficulties (~200/250) and around 50% to experience Insomnia Disorder (~125/250; Reeve et al., 2018a). It is difficult to estimate the rate of eligible persons who will be willing to participate and will be retained in the study. A sample of ~8 for use of the Sleepio intervention has been considered feasible in terms of study resource. Sample size throughout (e.g. recruitment, withdrawal, participation in follow-up) will act as implementation data. As the study is not designed to identify change in symptomatology measures, power calculations have not been carried out. We aim to recruit ~5 service users to participate in optional interviews.

6.6.1.2 Keyworkers

There are approximately 20 clinicians working as keyworkers in Esteem. We aim to recruit ~10 to interview.

6.6.2. Integration into the Esteem Service

Esteem are strongly in support of the project and are agreeable to their planned level of involvement in recruitment and monitoring. Evidence of management approval will be supplied. Two of the research applicants (AG and MS) work clinically in these services.

We plan to continue to present the study to the clinical staff teams and demonstrate the Sleepio application and Sleepio Clinic, in order to ensure keyworker familiarity and support for the project. Applicant MS provides supervision to keyworkers in Esteem for low intensity psychosocial interventions. Through this, she intends to support sleep enquiry and monitoring service user participants' use of Sleepio. Keyworkers will be provided with information about the study and their role as clinicians and as research subjects. We will offer an appointment with each keyworker to reflect upon their caseload and consider service users who may be appropriate to access the study and intervention.

6.6.3. Recruitment and Consent Procedures

6.6.3.1 Service Users

Keyworkers in Esteem FEP services will be approached to identify service users affected by sleep difficulties that may benefit from Sleepio. Service user participants will be recruited through their treatment as usual with their Esteem keyworker (sleep monitoring is part of this). Where service users report sleep difficulties, keyworkers will offer an information leaflet about the study and referral into the research study or contact details for researchers (study email address). Keyworkers will record that service users have agreed to keyworkers providing their details to researchers and to being contacted by the researchers in their casefile.

Those service users who wish to find out more about the study and meet eligibility criteria will be sent an easy-read Participant Information Sheet and Consent Form. They will be given the opportunity to ask questions and will be encouraged to speak to others about their potential participation (such as their keyworker). It will be made clear that in consenting to participate they are consenting to participate in sleep assessment, complete symptomatology measures pre- and post-intervention and use the Sleepio intervention. It will be made clear that participation does not affect their TAU. They will provide written consent if they wish to participate. Consenting service user study participants will receive access to Sleepio. They will register for the intervention with a researcher during the baseline symptomatology measures assessment session.

They will be given the option of additionally participating in semi-structured interviews prior to and after using the intervention, to talk about their expectations and experiences of Sleepio.

6.6.3.2 Keyworkers

As above, keyworkers will be introduced to and supported in their role in referring service users to the study and monitoring use of Sleepio through presentations, psychosocial supervision, and reflection sessions. Keyworkers will be provided with an easy read information sheet which clarifies their role as clinicians (attending a session to reflect on their caseload and service user suitability for the study and providing suitable service users with information about the study) and potentially as research participants (in semi-structured interviews) via email and letter. They will be given the opportunity to ask

questions and will be encouraged to speak to others about their potential interview participation (such as their colleagues). They will provide written consent if they wish to participate in semi-structured interviews, to talk about their expectations and experiences of Sleepio use in Esteem.

6.6.4 Randomisation

Service user participants will not be randomized to treatment. All service user participants will be provided with access to Sleepio. Research will focus on developing a model for the implementation of this intervention.

6.7 Data Collection

6.7.1 Implementation Data

We will gather data on eligibility, consent rates and the rate of service user participants beginning intervention. We will gather data on clinical sleep disorder assessment outcomes. Sleepio intervention will span week 0 to week 10. Usage data will be collated throughout these 10 weeks via the application. This data will comprise the rate of completion of the six sessions contained in the intervention and of sleep diaries. These metrics will allow us to ascertain intervention adherence, attrition and completion. We will further record rates of attendance to complete symptomatology measures. In analysis, these data will be represented by rates and summary statistics.

6.7.2 Measures

Symptomatology measures will be completed with service user participants using NHS Attend Anywhere or at in-person appointments at baseline (week -1), and at week 11. Researchers completing these appointments are NHS GGC employees with pre-existing access to Attend Anywhere. We will complete symptomatology measures using Online Surveys (<https://www.onlinesurveys.ac.uk/>; formally **Bristol Online Surveys**). Online Surveys is UK based, Data Protection Act 2018-compliant and has ISO certification. If sessions are undertaken in person, these measures will be completed on paper. The study researchers are not aware of any issues in relation to the suitability, ease of use or acceptability of these measures in this service user group. The baseline appointment will also allow participants to set up the Sleepio application and complete its initial assessment.

Service user participants will be assessed with measures of:

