5.1. Implementation

- 1) What is the rate of ineligibility and why?
- 2) What is the rate of consent into the study?
- 3) Can we characterise participant sleep disorder?
- 4) Do participants complete Sleepio initial assessment?
- 5) Do participants enter daily and weekly data?
- 6) How many sessions do participants complete?
- 7) What is the rate of attrition from intervention?

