6.5 Intervention

This study provides service users of Esteem with access to a digital CBTi application, 'Sleepio'. It aims to model factors of the implementation of this intervention in FEP services in NHS Scotland. Service user participants will be asked to continue to engage with their treatment as usual whilst accessing Sleepio. Esteem keyworkers will be involved in providing information and referral to the study for service users with sleep difficulties, then supporting service users' use of the intervention through the 'Sleep Clinic' online interface.

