6.5.2 Sleepio

Participating service users will receive access to a comprehensive sleep assessment carried out by researcher FR and to the Sleepio intervention. Sleepio is a dCBTi application which is personalised in response to input data (Espie et al., 2012). Sleepio's components are those common to CBTi interventions: i) Psychoeducation on sleep hygiene and processes; ii) cognitive components including restructuring, mindfulness, positive imagery, paradoxical intention training (trying to stay awake), and resolving thoughts about one's day; and iii) behavioural components including sleep restriction, stimulus control, and relaxation techniques. Sleepio is composed of six 20-minute

sessions presented by an animated therapist (“the Professor”), which are unlocked weekly. Participants complete an initial assessment (please see ‘Sleepio Onboarding Questions’) and chose a treatment goal, which drives initial personalisation of the application. Participants book digital ‘appointments’ with the Professor and receive prompts to complete these 6 sessions, to enter sleep data and to complete the Sleep Condition Indicator. The Sleepio algorithm tailors ongoing intervention based on this sleep data and other data about participants’ physical and mental health. Sleepio also provides access to online psychoeducation and a clinician-moderated user forum. Sleepio can be accessed via web browser (Safari or Google Chrome) or iOS smartphone. It cannot currently be accessed using an Android smartphone.

Keyworkers will be asked to monitor service users’ progress with using the Sleepio application. They will be provided with access to the ‘Sleep Clinic’ in order to support this role. The Sleepio Sleep Clinic is an online platform where health professionals can observe completion, data entered and Sleep Condition Indicator scores for service users they have clinical responsibility for. Service users will be made aware of keyworker access to this, prior to consenting to participate.

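### Does setting up Sleepio at a researcher-run visit spoil the question of whether participants complete its initial assessment?

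*Protocol*

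**What the plan says.** The implementation questions in Protocol Section 5.1 include, as the fourth, "Do participants complete Sleepio initial assessment". Section 6.5.2 refers the reader to a separate document, "Sleepio Onboarding Questions", for the content of that assessment.

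Two places describe how it is reached. Section 6.6.3.1 says of consenting service users: "They will register for the intervention with a researcher during the baseline symptomatology measures assessment session". Section 6.7.2 puts that session at week -1, by video link or in person, and adds: "The baseline appointment will also allow participants to set up the Sleepio application and complete its initial assessment".

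Section 6.7.1 lists the implementation data: eligibility, consent, the rate of starting the intervention, sleep assessment outcomes, and attendance for the symptom measures. Usage data come from the application over weeks 0 to 10: "This data will comprise the rate of completion of the six sessions contained in the intervention and of sleep diaries". Section 7.3.2 gives examples of the further pseudonymised data supplied by the app provider, in a list worded as open-ended.

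The keyworker's part is described separately. Section 6.5 states: "Esteem keyworkers will be involved in providing information and referral to the study for service users with sleep difficulties", followed by support through the Sleep Clinic interface. Section 6.6.3.2 describes the clinician role as "attending a session to reflect on their caseload and service user suitability for the study and providing suitable service users with information about the study".

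**The concern.** The study is meant to yield a logic model of how Sleepio would be implemented in a first-episode psychosis service. Registration with a researcher is a study procedure and lies outside the role described for keyworkers. If most participants complete the initial assessment while a researcher is present, a high rate could reflect attendance and assistance more than anything the service would see on its own. Neither Section 6.7.1 nor Section 7.3.2 lists a field for who helped or how much.

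The interviews look like a poor substitute. The service users' pre-intervention interview is at about week -2, before set-up, and the later one is at about week 12 and optional. If help at set-up is not noted at the visit, it may be hard to reconstruct, and the model might be silent on whether onboarding needs a researcher.

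**Working it through.** The protocol gives no figure for this rate, so there is none to reproduce. The check sets the sections side by side, with the little arithmetic that applies.

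**1. What is asked.** Question 4 in Section 5.1 is about completion. It does not mention unaided completion or onboarding by a keyworker. Neither the objectives in Section 5 nor the analysis in Section 6.9 undertakes to interpret the rate in that way.

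**2. What the procedure fixes.** Section 6.7.2 is permissive: the visit gives participants the chance to complete the assessment and does not require them to finish it there. In Section 6.6.3.1 the researcher's presence attaches to registration. Sections 6.5.2 and 6.7.2 both make the participant the one who completes the assessment. No section describes prompting, or a researcher completing it for someone. That the rate would mainly measure researcher-supported completion is therefore an inference, and the amount of help is unknown.

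**3. Whether the rate is sound as a description.** Inputs: about 8 service users (Section 6.6.1.1) and 95% confidence intervals for implementation measures (Section 6.9.1).
- Weight of one person: 1/8 = 12.5 percentage points.
- Exact (Clopper-Pearson) 95% intervals at n = 8, as illustration:

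| Completed | Rate | 95% interval |
|---|---|---|
| 8/8 | 100% | 63.1% to 100% |
| 7/8 | 87.5% | 47.3% to 99.7% |
| 6/8 | 75% | 34.9% to 96.8% |

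For 8/8 the lower limit is 0.025^(1/8) = 0.631. The intervals are wide because n is small, and they are the same whether or not anyone was helped. They say nothing about bias from assistance.

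**4. What the interviews can add.** Inputs: set-up at week -1 (Section 6.7.2), later interview at about week 12 (Section 6.7.3.1), about 5 of about 8 users sought (Section 6.6.1.1).
- Interval from set-up to the later interview: 12 - (-1) = 13 weeks.
- Users without an interview account: 8 - 5 = 3, or more if some of the 5 take only the earlier interview.

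These figures are right, but they do not show a defect. Section 6.7.3.1 samples post-intervention interviewees purposively across levels of engagement, so full coverage was never intended. About 10 keyworkers are also sought (Section 6.6.1.2). They are not said to attend set-up, but under Section 6.7.3.2 they can speak about their experience of Sleepio use in the service.

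**5. What covers use without the researcher.** The usage window in Section 6.7.1 is weeks 0 to 10 and so opens after the week -1 visit. The rate of beginning the intervention, the six sessions and the diaries are all planned data. Independent uptake would be read from these in any case.

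**6. What depends on question 4.** There is no threshold, progression rule or test. Section 6.9.1 reports implementation measures descriptively, and Section 6.9.3 feeds them with the interview data into the logic model.

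**The case for a change.** The strongest case for the concern is that it is about data capture and not analysis. If help is not noted at the visit, no later analysis plan can restore it. Section 11 says the logic model will inform the move of sleep treatment into usual care, and Section 8.2 recognises that some users may be distressed by technology. Whether a person needed help at first contact with the app would be useful to know. Help could also differ between video and in-person visits. Noting it would cost one item for each of about 8 people.

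Much of this stands as fact. Registration is with a researcher, no field for help is listed, and the usage data in Section 6.7.1 name sessions and diaries but not the initial assessment.

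It does not make the plan wrong. A field for help given is detail of a visit form, and neither the forms nor the interview schedule is shown. The provider data in Section 7.3.2 are given as examples, so a record of completion is not excluded. Section 7.2 makes one researcher responsible for collecting measures, interviewing, analysis and reporting. That overlap is not a systematic record, but it makes total loss of the information less likely. The information would be worth having, yet the protocol neither promises it nor needs it to answer question 4.

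**Conclusion.** The concern does not hold. Followed as written, the protocol gives a valid descriptive rate of completing the initial assessment under a procedure that it states openly. Use after the visit is measured separately. Nothing is contradicted or misstated, and the documents support no estimate of overstatement. What remains is a preference about one form item and about how the rate is labelled.

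This rests on two assumptions: that the rate is reported as completion at or after the baseline visit, in line with Sections 6.6.3.1 and 6.7.2, and that completion itself is recorded, as question 4 implies. A claim in the final report that the rate shows unaided or keyworker-led onboarding would go beyond the data, but the protocol makes no such claim.

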6.7.2.1 Insomnia

Service users will be screened for insomnia after completing consenting procedures, using the Sleep Condition Indicator – 2 Item (SCI-02; Luik et al, 2019). This is a reliable and validated shortened screening measure for insomnia, which correlates well to full

insomnia measures. Service users who's scores are not indicative of insomnia will be ineligible for study participation.

Insomnia symptoms will be assessed using the Insomnia Severity Index (Bastien, Vallieres, and Morin 2001) at baseline and week 11. This is a brief self-report questionnaire, designed to assess the severity of nighttime and daytime components of insomnia. It is widely used, demonstrates good reliability and validity, and is responsive to change through clinical treatment.

Additionally, participants will be regularly prompted within the Sleepio intervention to complete the full Sleep Condition Indicator (SCI, Espie et al., 2012). SCI is an 8-item scale which measures sleep problems against DSM-5 criteria for Insomnia Disorder. It has good validity and reliability and is sensitive to change (Espie et al., 2014). These scores will be available for analysis by researchers.

6.7.2.2 Mental Health Symptomatology

Psychotic symptoms will be assessed using the Specific Psychotic Experiences Questionnaire; hallucinations subscale (SPEQ(H), Ronald et al., 2014) and Revised Green et al Paranoid Thought Scales (R-GPTS, Freeman et al., 2019). The SPEQ is a transdiagnostic self-report measure of psychosis symptomatology, which comprises subscales of paranoia, hallucinations, cognitive disorganization, grandiosity, anhedonia, and parent-rated negative symptoms. The R-GPTS is a two-factor measure of paranoid thoughts, with subscales distinguishing persecutory ideation and ideas of social reference.

Mood symptoms will be assessed using the Depression, Anxiety and Stress Scales 21 item (DASS-21, Lovibond and Lovibond, 1995; Anthony et al., 1998). The DASS-21 is a widely used measure assessing symptoms of depression (low positive affect, low self-esteem, hopelessness), anxiety (physiological symptoms, situational anxiety), and stress (negative affect, tension, agitation).

Covid19 worry will be assessed using the Fear of Covid19 Scale (Ahorsu et al., 2020). This scale is new but has relatively good metrics and has been validated in several populations.

6.7.3 Qualitative Interviews

6.7.3.1 Service Users

Service users will be provided with the *option* to participate in semi-structured interviews prior to beginning intervention and/or after completing the intervention. Each interview appointment will last ~45 - 60 minutes. Pre-intervention interviews will be undertaken prior to the baseline symptomatology measures appointment, at approximately week -2. They will focus on service users' expectations for the Sleepio intervention (see Interview Schedule).

Post-intervention interviews will be undertaken after completing follow-up symptomatology measures, at approximately week 12. They will focus on service users' experiences of the Sleepio intervention (see Interview Schedule). Post-intervention, participants will be purposively sampled to include a range of service users reflecting their engagement with the Sleepio App.

Interviews will be undertaken using a NHS Microsoft Teams meeting from an NHS GGC computer or in-person at an Esteem base. Attend Anywhere cannot be used as it is not possible to record on this platform. As with Attend Anywhere, researchers have pre-existing access to this as NHS GGC employees and it is considered secure for NHS use. Interviews will be digitally video recorded and auto-transcribed for purposes of analysis. These are inbuilt features of Microsoft Teams meetings. If interviews take place in person, data will be collected in the form of audio recordings on an encrypted recording device and transcribed by researcher FR.

Service users can participate in pre- or post-intervention interviews, or neither.

6.7.3.2 Keyworkers

Keyworkers in Esteem will be offered the opportunity to participate in semi-structured interviews prior to service users beginning intervention and/or after all service users have completed the intervention. Each interview appointment will last ~45 - 60 minutes. Pre-intervention interviews will focus on keyworkers' expectations for the Sleepio intervention (see Interview Schedule).

Post-intervention interviews will focus on keyworkers' experiences of the Sleepio intervention use in Esteem (see Interview Schedule).

Interviews will be undertaken using a NHS Microsoft Teams meeting from an NHS GGC computer or in-person at an Esteem base. As above, interviews will be digitally video or audio recorded and transcribed for purposes of analysis.

Keyworkers can participate in pre- or post-intervention interviews, or neither.

6.8 Participant Withdrawal

All participants will have the right to withdraw from the study at any time. It will be clearly stipulated at the time of consent that they have this right and that withdrawal will not affect their clinical treatment (service users) or role in Esteem (keyworker participants).

Withdrawal from the study can be at the request of the participant or at the discretion of the researchers. Withdrawn participants will be informed that they will no longer continue with the study protocol and that their withdrawal from the study will not influence their treatment/role within the service. Research data collected up to the time of withdrawal against anonymous participant IDs or Sleepio access IDs will be retained for use in the study. Video or audio recordings collected up to the time of withdrawal will be retained

for use in the study and transcription. Consent forms will be retained. Other non-anonymized or personal data will be destroyed should a participant withdraw from the study. All of this is made clear to interested persons prior to consenting to participate.

Service user participants may also choose to stop using the Sleepio intervention, without withdrawing from the study. These participants would still be asked to participate in the post-intervention assessment session and be given the option of participating in post-intervention interviews. This will be made clear to interested persons prior to consenting in the Participant Information Sheet.

The sponsor reserves the right to terminate the study at any stage for any reason, including funding considerations. Existing participants will be informed of the termination of the study and will be followed-up as part of their TAU clinical management.

6.9. Statistical Analysis

The main aim of the implementation study will be delivered via the development of a logic model describing the potential implementation of Sleepio within FEP services in NHS Scotland.

